1. STUDY OBJECTIVES/HYPOTHESIS

We hypothesize that low levels of fitness and MVPA result in impaired metabolic function in adolescents. For this pilot study, we will quantify variations in metabolic characteristics using a 2 x 2 cross-sectional study design, stratified by bodyweight (normal vs overweight/obese) and physical activity (sedentary vs. active). Our goal is to identify metabolic factors that influence the energy balance system to directly inform interventions designed to prevent or reduce the prevalence of pediatric obesity.

Aim 1: To quantify the independent effects of physical inactivity and obesity on metabolic responses at rest, after a meal, and during exercise using indirect calorimetry.

Aim 2: To determine whether physical activity level impacts appetite control independent of obesity status via metabolic function.

Aim 3: To explore the hormonal and neurocognitive mechanisms of appetite control.

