4. TARGET STUDY POPULATION SPECIFICS

Participants will include 60 adolescent males (aged 14-18 years, Tanner stages III- IV), equally enrolled based on physical activity and body weight status (**Table 1**).

Table 1. Enrollment criteria based on physical activity and body weight status

Adolescents males (age 14-18 years & Tanner stages III- V)	Normal weight ($\geq 5^{\text{th}}$ to $< 75^{\text{th}}$ percentile)	Overweight/obese ($\geq 85^{\text{th}}$ to $< 99^{\text{th}}$ percentile) ⁴¹
Inactive (<30 min/day MVPA)	n= 15	n= 15
Active (>60 min/day MVPA) ⁴²	n= 15	n= 15

Inclusion Criteria

- Males (Tanner Stage III-IV), ages 14-18
- Weight stable ($\pm 5\%$ weight change) over the previous three months as assessed by self-report.
- BMI $\geq 5^{\text{th}}$ and $\leq 99^{\text{th}}$ percentile
- Physically healthy for exercise as assessed by self report Physical Activity Readiness Questionnaire (PAR-Q) for children.
- For fMRI testing, all participants must be right handed and must have normal or corrected to normal vision (as they will be viewing pictures in the fMRI procedure).

Exclusion Criteria

- History of restrained eating, eating disorders, bariatric surgery, or other significant medical diagnosis that could impact metabolism.
- Participants taking thyroid medications, beta blockers, or other stimulants (medications are known to affect physical activity level and metabolism).
- Due to fMRI procedure requirements, children with a history of Attention Deficit Hyperactivity Disorder (ADHD) or other diagnosed psychiatric issues will be excluded.

[figure not shown]

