7. STATISTICAL CONSIDERATIONS

Measures

- Primary measures: Metabolic function and body composition
- Secondary measure(s): Demographics, appetite, food cravings, and eating behaviors, lifestyle assessment, fMRI, energy intake

General Design Issues

The proposed pilot study consists of a 2 x 2 cross-sectional study design, which will maximize statistical power despite a small sample size. This pilot study will generate data needed for a larger study.

Sample size determination

As a pilot study, we will have resources to collect data from N=60 participants. We will use this data to determine power requirements for a larger study.

Data Analyses

Statistical significance for comparison between groups will be tested using analysis of variance (ANOVA) for continuous variables and chi-square tests for categorical variables. Statistical significance will be set at P<.05 (two-sided) for all analyses.

fMRI Analysis. We will estimate several general linear models (GLMs). All of the models allow for first-order auto regression and included six motion parameters,

constants, and linear time trends for each run as regressors-of-non-interest. A two-stage mixed-effects analysis will be performed in which the regression coefficients for each condition of interest will be tested across participants via t-tests. Two-tailed tests are used for all statistical analyses. We will perform multiple comparison corrections at the cluster level using Monte Carlo simulations with the AlphaSim program.

EMA-Food Craving Analysis. A regression model will test whether mean EMA ratings of anticipation (craving) and reward (pleasantness rating, ate more than intended, ate beyond satiety) are correlated with postprandial glucose surge and area under the curve for glucose following the standardized lab meal.

We will use a hierarchical mixed model to examine the nested association between EMA-measured craving, food pleasantness, and overeating *within* eating episodes in free-living conditions. Pre-meal craving and within-meal pleasantness ratings will be used as predictors in models with overconsumption rating post-meal. Food photos will be used to distinguish HF from non-HF (fat/carb: 25%+/25%+; sweet/fat: 15-35%/30%+; salt-fat: 0.5-2.5%/10-35%) using the detailed NDSR nutrition data output we will receive from the app.

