We will conduct a series of Pearson correlations to test whether craving and reward symptoms measured in the standardized meal and free-living conditions are significantly correlated.

We will use a linear regression model to test the degree to which anticipation (craving) and reward (food enjoyment, eating despite satiety) as measured using photo-EMA, and intensity of glucose surge during the standardized lab meal will be associated with % fat mass and visceral adipose tissue as measured using DXA.

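### The regression of EMA craving and reward on the glucose response has no term for weight group or activity group, so it cannot support a reading independent of obesity or activity

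*Protocol*

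**What the plan says.** Protocol Section 1 describes a 2 x 2 cross-sectional design "stratified by bodyweight (normal vs overweight/obese) and physical activity (sedentary vs. active"). Section 4 says participants are "equally enrolled based on physical activity and body weight status", and Table 1 sets 15 boys in each cell. The table leaves out boys between the 75th and 85th BMI percentiles and those with 30 to 60 minutes of MVPA a day. Aims 1 and 2 both seek to separate activity from obesity; Aim 2 does so for appetite control.

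Section 7 assigns ANOVA and chi-square tests to comparisons between groups. It then lists three association analyses on subject-level measures:

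- **EMA-glucose regression.** It tests whether mean anticipation and reward ratings "are correlated with postprandial glucose surge and area under the curve for glucose following the standardized lab meal".
- **Lab-to-home correlations.** "We will conduct a series of Pearson correlations" between craving and reward in the standardized meal and in free living.
- **Adiposity regression.** It tests the degree to which EMA anticipation and reward, together with the glucose surge, "will be associated with % fat mass and visceral adipose tissue as measured using DXA".

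None of the three names weight group, activity group, their interaction, a within-group analysis or any other covariate. The SAP repeats the same text, and neither document has a general statement on covariate adjustment.

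**The concern.** Suppose overweight boys both crave more and have a larger glucose response, while craving and glucose are unrelated among boys of the same weight and activity group. The pooled regression would still tend to show a positive slope. That slope restates two group differences and says nothing about craving and glucose beyond them.

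This matters because the aims ask for effects separated from obesity or activity, and Aim 3 speaks of mechanisms of appetite control. The pooled regression cannot carry such a reading. Section 7 also says the pilot data will be used to plan a larger study, so a coefficient that mixes between-group and within-group association could pass into that design.

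**Working it through.** **Inputs from the documents.** Four cells of 15 give 4 x 15 = 60, which matches Section 7 ("As a pilot study, we will have resources to collect data from N=60 participants"). The level is 0.05, two-sided, for all analyses.

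**Assumed inputs.** The documents give no group differences in craving, reward or glucose. I take shifts of 0.3 to 1.0 within-group SD and show the range. I treat a single pair of variables; the planned regression has several EMA ratings, so the figures are illustrative.

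**Step 1: pooled correlation when the within-group correlation is zero.** If one balanced two-level factor shifts the variables by a and b SD,

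r = (ab/4) / sqrt[(1 + a²/4)(1 + b²/4)].

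For a = b = 0.8: 0.16 / 1.16 = 0.138. For a = b = 1.0: 0.25 / 1.25 = 0.20.

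**Step 2: rejection rate.** With 60 boys the test has 58 df and a critical |r| of 0.254. Simulation with four cells of 15 and no within-cell association gives:

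| Shift in both variables, one factor | Pooled r | Unadjusted test rejects | Both factors added |
|---|---|---|---|
| 0 | 0 | 5% | 5% |
| 0.3 SD | 0.02 | 5% | 5% |
| 0.5 SD | 0.06 | 7% | 5% |
| 0.8 SD | 0.14 | 18% | 5% |
| 1.0 SD | 0.20 | 34% | 5% |

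**Step 3: sensitivity to the pattern of shifts.**

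- One variable shifted by 0.2 SD and the other by 0.5 to 1.0 SD: about 5% to 6%.
- Two factors of equal strength, one pushing the correlation up and the other down: the contributions cancel and the test rejects about 4% to 5% of the time.
- Both factors shifting both variables the same way: 13% at 0.5 SD and 48% at 0.8 SD. This needs four aligned shifts and is an outer case.

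**Step 4: is the quota sampling the cause?** Take BMI z-score as standard normal in the reference population. Mixing the 5th-75th and 85th-99th percentile bands equally gives a variance of about 1.03, so the quotas hardly stretch the range. Now let two variables depend linearly on BMI z-score and otherwise be independent, with group gaps of 0.5, 0.8 and 1.0 SD. The unadjusted test rejects 9%, 26% and about 49% of the time in the quota sample. In a random sample from the reference population the rates are 8%, 25% and 45%. In one limited to the 5th-99th percentiles they are 7%, 17% and 31%. Most of the effect of weight is ordinary confounding, present without quotas.

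**Step 5: the adiposity outcome.** On the same assumption the two weight groups differ by 1.78 in mean BMI z-score. The share of variance between groups is (1.78/2)² / 1.03, or about 77%. Weight group is therefore a coarse version of the outcome wherever % fat mass and visceral fat track BMI.

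**Step 6: cost of adjustment.** For one pair of variables, residual df fall from 58 to 56 (55 with the interaction). At a true within-group correlation of 0.35, power falls by one to two percentage points from about 80%.

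**The case against.** The strongest reply is that the plan asks marginal questions: whether things are correlated or associated. If craving and glucose both rise with weight, the marginal correlation is real and rejecting is no error. That stands. The rates above are errors only against a within-group null that the documents never state, so a reader should not take them as the plan's false-positive rate.

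Four further points also stand, wholly or in large part:

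- **Cause.** A reader might infer that enrolling by quota manufactures the correlations. Step 4 does not support this for weight. The balanced cells also keep weight and activity from being confounded with each other.
- **Lab-to-home correlations.** These compare related measures in two settings. Boys who crave more in both are showing agreement, including where the difference runs along group lines. The raw coefficient is a legitimate planned quantity and should not be replaced.
- **Adiposity regression.** A difference in craving between weight groups is part of the association being tested. Adjusting for weight group would remove much of the outcome's variance, and a within-group slope works on a restricted range.
- **Silence.** The models are given in outline, and the plan never says they are unadjusted. Covariates could be added later, but nothing in either document commits to that.

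What the reply does not meet is the gap between the aims and the EMA-glucose model. A marginal association cannot answer a question posed as independent of obesity or activity.

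**Conclusion.** The point holds for the EMA-glucose regression, as a low-cost improvement to a secondary analysis in a pilot. As specified, a significant result may reflect only group differences in both craving or reward and glucose.

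The size is uncertain because it rests wholly on assumed shifts. With one factor acting in the same direction on both variables, rejection of a zero within-group association runs from about 5% at 0.3 SD to 34% at 1.0 SD. It stays near 5% if either shift is small or the factors oppose each other.

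A reader might go further and infer that all three association analyses are invalid, or that the sampling scheme creates spurious findings. The documents do not support either. The lab-to-home correlations and the pooled adiposity slope answer sensible questions as planned and need only supplementary estimates. The primary measures, metabolic function and body composition, have their own ANOVA group comparisons, which this point does not touch.

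**What to change.** Add to the SAP, and to Section 7 of the protocol:

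- **EMA-glucose regression:** include weight group and activity group as covariates, and report the unadjusted result beside the adjusted one. State that only the adjusted estimate bears on association within groups.
- **Lab-to-home correlations:** keep the Pearson correlations as the agreement measure, and report partial (within-group) correlations beside them.
- **Adiposity regression:** add activity group and keep the pooled slope as planned. Show the within-weight-group slope only as a supplement, with a note that it answers a different question on a restricted range.

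Both factors are already recorded at enrollment, so no new data are needed. The cost is two degrees of freedom in the EMA-glucose model, a slight loss of power and a few more reported estimates.

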8. HUMAN SUBJECTS

Institutional Review Board (IRB) Review and Informed Consent

The IRB of record is Children's Mercy Hospital.

This protocol, and any subsequent modifications, will be reviewed and approved by the Pediatric IRB at The Children's Mercy Hospital & Clinics.

Potential participants will be recruited from our various weight management programs at the Center for Children's Healthy Lifestyles & Nutrition (CHLN), from our electronic medical records at Children's Mercy Hospital and the University of Kansas Medical Center, and from the community. We plan to use the available patient registries at CMH and KUMC to mail our recruitment materials to a random number of patients who meet the inclusion/exclusion criteria. We will also place out recruitment materials in the Primary Care clinics at CMH and KUMC. Recruitment materials will be distributed in the community through our partners via the Weighing In and Healthy Lifestyle Initiative listserves. Based on past experience recruiting for similar studies, we anticipate needing

174 initial contacts and 82 screens + dropouts to achieve our goal of 60 completed participants.

Parents of potential subjects will contact the study team using the phone number or email address on the recruitment flyer. The study team will do a 10 minute phone screening with the parent to determine eligibility, and will schedule a time for the parent and child to come in for an orientation. The parent and child will then come to the Don Chisholm center at CMH for an orientation. The consent form will be reviewed and ample time will be given for the parent and child to consider participation. Prior to drawing any blood or performing any other procedures related to this study, the permission/assent form or consent form will be reviewed carefully with the participant and parent in person. If the parent and child agree to participate, further screening questions will take place. The family will then schedule a time to come in for the measurement session (Visit 2).

Subject Confidentiality

All records will be kept in a locked file cabinet. Human subject's names will be kept on a password protected database and will be linked with a study identification number for this research. All computer entry and networking programs will be done using study identification only. All data will be entered into a computer that is password protected. Data will be stored in a locked office of the investigators and maintained for a minimum of three years after the completion of the study.

Subject Payment

Subjects will be paid via ClinCard \$75 when the activity monitors are returned at visit 3 and upon completion of the study at visit 4. Total payment per subject is \$150. SSN is required for payment, and will be entered directly into the Greenphire secure website. SSN will not be retained in the subject's study file.

9. PUBLICATION OF RESEARCH FINDINGS

- Results are intended to be presented at pediatrics or physical activity-related conferences by the study team within the next year.
- Results are intended to be published in a physical activity or public health journals.

STATISTICAL ANALYSIS

Statistical significance for comparison between groups will be tested using analysis of variance (ANOVA) for continuous variables and chi-square tests for categorical variables. Statistical significance will be set at $P < .05$ (two-sided) for all analyses.

fMRI Analysis. We will estimate several general linear models (GLMs). All of the models allow for first-order auto regression and included six motion parameters, constants, and linear time trends for each run as regressors-of-non-interest. A two-stage mixed-effects analysis will be performed in which the regression coefficients for each condition of interest will be tested across participants via t-tests. Two-tailed tests are used for all statistical analyses. We will perform multiple comparison corrections at the cluster level using Monte Carlo simulations with the AlphaSim program.

EMA-Food Craving Analysis. A regression model will test whether mean EMA ratings of anticipation (craving) and reward (pleasantness rating, ate more than intended, ate beyond satiety) are correlated with postprandial glucose surge and area under the curve for glucose following the standardized lab meal.

We will use a hierarchical mixed model to examine the nested association between EMA-measured craving, food pleasantness, and overeating *within* eating episodes in free-living conditions. Pre-meal craving and within-meal pleasantness ratings will be used as predictors in models with overconsumption rating post-meal. Food photos will be used to distinguish HF from non-HF (fat/carb: 25%+/25%+; sweet/fat: 15-35%/30%+; salt-fat: 0.5-2.5%/10-35%) using the detailed NDSR nutrition data output we will receive from the app.

We will conduct a series of Pearson correlations to test whether craving and reward symptoms measured in the standardized meal and free-living conditions are significantly correlated.

We will use a linear regression model to test the degree to which anticipation (craving) and reward (food enjoyment, eating despite satiety) as measured using photo-EMA, and intensity of glucose surge during the standardized lab meal will be associated with % fat mass and visceral adipose tissue as measured using DXA.
